Document Coversheet

Study Title: Assessment of Medication Optimization in Rural Kentucky Appalachian Patients With Mild Cognitive Impairment or Dementia: The AMOR Kentucky Study

Institution/Site:	University of Kentucky
Document (Approval/Update) Date:	10/12/2020
NCT Number:	NCT05078437
IRB Number	69305
Coversheet created:	6/12/2024

Study overview: The current proposal includes a single arm, unblinded feasibility study of the MTM describing intervention in rural/underserved Kentucky Appalachian populations with MCI and/or dementia. Our well-established experience in providing MTM deprescribing interventions to the aging population with and without cognitive decline has allowed us to develop routine practices of assessment of medication appropriateness using the MAI, as well as implementation of a multidisciplinary physician-pharmacist team targeting improvement in cognitive outcomes in the aging population. This approach will be carried forward through a telemedicine practice that is comprised of approximately 500 patient-caregiver dyads throughout rural areas of Appalachian Kentucky. The methods for cognitive assessment and assessment of other health related issues have been well-established through an initial grant from the Alzheimer's Association in 2007 and have been in practice for 16 years here at UK.

We intend to use this system and these experiences to assess medication appropriateness in 50 research participants over the one-year funding. In this trial, each participant will be evaluated for medication appropriateness, and a deprescribing intervention will be provided by our multidisciplinary team.

Reassessment of the proposed medication changes, as well as the potential impact on cognition will be determined at the six-month evaluation for each of these participants. Participants will be age greater than 60 years, with mild cognitive impairment, and/or in the early stages of dementia. Participants will be enrolled and followed for 6 months to determine the impact of the telemedicine-delivered deprescribing intervention in improving medication-related outcomes (i.e., medication appropriateness, number of medication/PIM) in rural/underserved Kentucky Appalachian populations with cognitive impairment and/or dementia. As secondary outcome measures, we will evaluate the impact of the deprescribing intervention on cognitive function and caregiver burden using validated assessment instruments (see description of outcome measures below).

Study Design. This preliminary feasibility study will use an unblinded, single-arm design. See study table for timing of specific procedures and intervention (Table 3).

Study population. Participants will all be enrolled from rural Appalachian referrals to the UK telemedicine Cognitive Clinic. All people enrolled in this clinic receive a standardized cognitive evaluation and treatment plan, described below. Immediately after completing their first remote visit, eligibility for participating in the study intervention – which comprises specific medication-focused evaluation and recommendations, also described below – will be assessed. Eligibility includes: (1) 60 years or older, (2) diagnosed with mild cognitive impairment or dementia, (3) using at least one PIM, (4) living in the community, (5) willing to participate in this intervention study (both the patient and the caregiver). Subjects meeting eligibility criteria will be contacted, informed about the study, and invited to participate. The informed consent process will be performed remotely with the participant and or legally authorized representative using IRB-approved protocols (see Human Participants Section for details).

AMOR-KY MTM Intervention. The proposed deprescribing intervention is using a patient-centered framework by: (1) balancing the risks and benefits, and addressing the specific needs of each individual patient, (2) considering the individual patient and their caregiver's preferences and values, and (3) empowering the patient and their caregiver to take responsibility and fully participate in the decision-making process as equal team players.²⁸⁻³⁰ The proposed MTM deprescribing intervention will be developed on an individualized basis, taking into account specific medications and medical conditions for each unique participant, and delivered in an interdisciplinary fashion by the pharmacist-physician team working closely with the patient and their caregiver.

After enrollment, we will conduct an interview with the participant and their caregiver to collect information on all the medications the participant is taking, including prescription and over-the-counter medications, vitamins and supplements. These data will include health history, indication for treatment, duration of therapy, dose and mode of administration, and adherence to therapy. In addition, we will assess the potential for adverse drug effects by asking the participant and their caregiver to recall any side effects, unwanted reactions, or other problems with their medications in the last year or since the medication was initiated, whichever is shorter.³¹ For patients reporting adverse effects, additional information will be collected to include the name of the

Table 3. Timeline of study events

Study procedures	Baseline evaluation	4 weeks	3 months	6 months
Complete medical evaluation	X			X
MTM intervention		X	X	
Assessment of medications	X	X	X	X
Assessment of AE/SAEs		X	X	X
Participant outcome measures	X			X
Caregiver outcome measures		X		X

Abbreviations: MTM, Medication Therapy Management Intervention; AE, adverse event; SAE, serious adverse event.

medication they suspected, a description of the symptomatology experienced, and whether they modified the use of the medication in question on their own or after discussing with their primary care physician.³¹

Based on the data collected, the pharmacist will review the information and will prepare prioritized written recommendations to include the 'problem-list' of medications that are potentially inappropriate (based on indication, adverse events, drug-drug or drug-disease interaction, or as described by the Beers 2019 criteria, specifically focusing on medications like anticholinergics, benzodiazepines, or Z-drugs that are of importance to patients experiencing MCI or dementia).^{36,37} The pharmacist will also provide recommendations on the proposed action for each of these medications including: 1) discontinuation; 2) modification of therapy to switch to suggested safer alternative, or to change the dose; or 3) continuation of treatment due to treatment necessity and favorable outcomes under treatment. Where appropriate, the proposed alternatives will include medications listed in an adjunct to the Beers 2019 criteria as "Alternative Medications for Medications in the Use of High-Risk Medications in the Elderly and Potentially Harmful Drug-Disease Interactions in the Elderly Quality Measures".³⁶⁻³⁸

Following this review, the pharmacist-physician team will meet during case conferences to discuss all the problems identified and decide on final recommendations for discontinuation or change related to inappropriate medications. The final recommendations and their rationale, along with general drug information will be discussed by the pharmacist with the patient and their caregiver. Attention will be given to explaining the rationale behind each recommendation and allowing the patient and the caregiver to ask clarification questions, and to express concerns. The written recommendations and the proposed changes will be shared with the patient's primary care physician who will be consulted on the best approach to improve the patient's outcomes. At 4 weeks and 3 months after the initial intervention was delivered, we will follow up with the participant and their caregiver to determine the need for additional evaluations by the pharmacist and/or physician. If necessary, the pharmacist-physician team will provide the following for the participant: (1) comprehensive medication list, updated each time there is a medication change; (2) monitoring for patient concerns or adherence issues; (3) targeted additional evaluation and recommendations for interim medication changes. The intervention will be administered using the existing tele-medicine infrastructure at UK.

Table 4. Description of components of the standard telemedicine evaluation used in this proposal	
Instrument	Description & Rationale
Alzheimer disease 8 questions scale (AD8)	Brief 8 item screening questionnaire validated for the detection of MCI and/or dementia
Past Medical History	Includes medical/surgical/family/social history components of the standard clinical evaluation. Used to determine MAI and identify covariates
Neuropsychiatric inventory (NPI)	Used to assess behavioral and psychiatric symptoms of dementia. These may serve as exploratory measures and are important for AE/SAE issues.
Functional Assessment Questionnaire (FAQ)	Used to assess functional consequences of MCI/dementia. These may serve as exploratory measures and are important for AE/SAE issues.
Kokmen Short Test of Mental Status (KSTMS)	Global assessment of cognitive function that allows cross comparisons between other commonly used global assessment tools such as the Folstein Mini-Mental State examination (MMSE) and the Montreal Cognitive Assessment (MOCA). Used to define cognitive state, diagnosis, and to track longitudinal change.
5 Word Free & Cued Recall Test	Memory test that assesses learning, free-delayed recall, and recall augmented by category and choice cuing. Used to define memory components, assist with diagnosis, and to track longitudinal change.
Category Fluency (animal naming)	Number of animals one can name in 60 seconds. Semantic fluency measure used to assess verbal capacity that has been shown to have high predictive ability for early clinical cognitive decline and for tracking longitudinal change.
Phonemic Fluency (letter fluency)	Number of words starting with the letter "S" one can name in 60 seconds. Phonemic fluency measure used to assess verbal capacity that has been shown to have high predictive ability for early clinical cognitive decline and for tracking longitudinal change.
Physical Examination	Extraocular movements, AMRs (alternating motion rates) in all 4 extremities, Praxis in all 4 extremities, Gait and postural stability, Frontal release signs (glabellar, snout, palmomental).
Clinical Dementia Rating (CDR) scale	The CDR is a fundamental staging system for MCI and dementia stage determination including both global as well as sum of box scores spanning 6 domains of cognition and function. Scores will allow determinations of inappropriate medication use and success of the intervention as well as serving as a covariate in the secondary and exploratory and outcome measures described.

Telemedicine Evaluation Protocol. All study participants will receive the standard telemedicine evaluation for the UK Telemedicine Cognitive Clinic, which includes a 1-hour initial visit and a 30 minute follow up telemedicine evaluation (as noted above, after the first clinic visit, patients will be evaluated for eligibility for the "add-on" MTM intervention we seek to study, and thereafter invited to participate in this research). In the initial evaluation, a diagnosis is made or diagnostic testing is pursued, which may include routine laboratory blood tests to evaluate for reversible causes of dementia and brain imaging studies (CAT scan or MRI) according to the AAN practice parameter on the initial workup and diagnosis of dementia (AAN practice parameter on initial evaluation of dementia). Details of the standard telemedicine evaluation used in this study are provided in Table 4. These assessment scales are ideal for telemedicine assessment providing insights into diagnosis as well as gait, balance and fall risk that are important outcomes of deprescribing interventions. They will serve as appropriate clinical diagnostic and research outcome measures supporting the proposed protocol.

Following the Telemedicine evaluation, a tentative diagnosis will be made in relation to the research participant's cognitive status, that will be used as an important covariate in the analysis. Ultimate clinical diagnosis and disease staging will follow currently approved National Alzheimer Coordinating Center criteria and guidelines.

Outcome variables (Aims 1 and 2).

Primary outcomes of interest include change from baseline to the 6 months follow-up in the **Medication Appropriateness Index (MAI)** and in **number of medications** (total number and number of PIM), with a focus on medications targetted by the MTM deprescribing intervention. MAI rates each medication based on 10

different criteria (Table 5), each of them with explicit instructions and examples to guide evaluation; the evaluator rates whether the particular medication is "appropriate", "marginally appropriate", or "inappropriate".³⁹ The reliability of MAI assessments made by a clinical pharmacist and a physician (i.e., internist and geriatrician) demonstrated high inter-rater ($\kappa = 0.83$) and intra-rater reliability ($\kappa = 0.92$).³⁹ We will also measure the reduction in the number of potentially inappropriate medications,³⁶ from baseline to the end of the study period. **Secondary outcome measures** will include deprescribing and caregiver assessments to explore the acceptability of deprescribing and caregiver burden that may be associated with inappropriate medication use and the correction of potential medication misuse that may be influenced through our interventional strategy (Table 6); these will also be collected at the beginning and end of the study (see Table 3). Additional secondary and exploratory outcome measures include **cognitive assessments** collected as part of the routine telemedicine cognitive assessment are described earlier. To assess **acceptability of the intervention**, at the last study visit, patients and caregivers will be surveyed using several Likert scale questions and will be given the opportunity to share their opinions of the intervention, including what they liked and disliked about it and what they might do differently.²⁴ Responses to this survey will be used to inform the planned subsequent iteration of the study for a major future RCT.

Statistical Analysis Plan and Power Calculations:

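### Table 3 shows no initial MTM delivery and no time zero is stated, so the first caregiver measure may fall after the intervention starts and the AE/SAE intervals are undefined

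*Combined protocol and SAP*

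**What the plan says.** The Study Design paragraph makes Table 3 the reference for timing: "See study table for timing of specific procedures and intervention (Table 3". The table has four columns: baseline evaluation, 4 weeks, 3 months and 6 months. Its relevant rows are:

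- **MTM:** the row reads "MTM intervention X X", with the marks under 4 weeks and 3 months. Baseline and 6 months are blank.
- **Safety:** the row reads "Assessment of AE/SAEs X X X", with the marks under 4 weeks, 3 months and 6 months.
- **Caregiver outcome measures:** marked at 4 weeks and 6 months. Participant outcome measures are marked at baseline and 6 months.

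The AMOR-KY MTM Intervention section gives a sequence without dates. After enrollment there is an interview, then a pharmacist review, a case conference, and a discussion of the recommendations with patient and caregiver. Follow-up contacts come "At 4 weeks and 3 months after the initial intervention was delivered", and further recommendations are made only if needed.

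The section Outcome variables (Aims 1 and 2) defines the primary endpoint: "Primary outcomes of interest include change from baseline to the 6 months follow-up". It also says that the deprescribing and caregiver assessments are collected at the start and the end of the study, and cites Table 3 for this.

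**The concern.** The text has three MTM events: one delivery and two contacts counted from it. The table has two, and neither is labelled as the initial delivery. The reader therefore cannot tell whether MTM starts near the baseline evaluation or at the 4-week visit.

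Three things depend on the answer:

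- **Caregiver measures.** Their first value is taken at 4 weeks. If MTM has already been delivered, that value is not a pre-intervention one, and the signed-rank comparison of pre- and post-intervention values misses any change in the first weeks. Table 6 adds that the rPATD answers are meant to shape the approach to deprescribing, which presumes that they are available before recommendations are made.
- **Safety follow-up.** The interval from first MTM to the next AE/SAE check depends on the start. The recommendations can include stopping or changing drugs, so this interval should be known.
- **Time on intervention at 6 months.** The effect-size estimate is meant to support a larger study, and its reader will need to know how long after first MTM it was measured.

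**Working it through.** The plan gives no figure for time on intervention, so there is none to reproduce. Its one power figure (34 participants for a mean MAI change of 1.0) does not use visit timing, and neither it nor the enrollment target of 50 changes here.

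**Inputs.** Table 3 visits at 4 weeks, 3 months and 6 months; text contacts at 4 weeks and 3 months after initial delivery. Assumptions: 3 months = 13 weeks and 6 months = 26 weeks. Let *d* be the number of weeks from baseline to first MTM delivery. The documents do not give *d*. It cannot exceed 4 if Table 3 is respected, because MTM is marked there at week 4.

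**Formulas, with Table 3 visits counted from baseline**

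- First MTM to endpoint = 26 − *d*
- Gap between that and a week-4 start = [(26 − *d*) − 22] / (26 − *d*)
- Text contacts fall at weeks *d* + 4 and *d* + 13
- Next AE/SAE check after first MTM = 4 − *d* if *d* is below 4. If *d* = 4, the week-4 check shares the visit with first MTM and the next is 13 − 4.

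| *d* (weeks) | First MTM to endpoint | Gap against week-4 start | Text contacts (weeks) | Next AE/SAE check after first MTM | First caregiver measure |
|---|---|---|---|---|---|
| 0 | 26 | 4/26 = 15% | 4 and 13 | 4 weeks | 4 weeks after first MTM |
| 1 | 25 | 3/25 = 12% | 5 and 14 | 3 weeks | 3 weeks after |
| 2 | 24 | 2/24 = 8% | 6 and 15 | 2 weeks | 2 weeks after |
| 4 | 22 | 0% | 8 and 17 | 13 − 4 = 9 weeks | same visit, order not stated |

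**If the columns are counted from first delivery instead.** First MTM to the 6-month visit is 26 weeks whatever *d* is. The text contacts coincide with the 4-week and 3-month columns, and the next AE/SAE check is 4 weeks after delivery. The first caregiver measure is then also 4 weeks after delivery.

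**Side by side.** If *d* = 4, the caregiver measure can precede MTM, but the text's contacts at weeks 8 and 17 have no Table 3 visit. If delivery is near baseline, or the columns run from delivery, the contacts fit the table exactly or nearly so. Table 3 then omits the main delivery, and the caregiver measures start after it. No reading of the documents as written makes the table, the text's contacts and the collection of caregiver measures at the start of the study all agree.

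**The case against.** The strongest reply is that Table 3 states no time origin. Its 4-week and 3-month columns match the text's two contacts, so the simplest reading is that these are the same contacts and the table merely lacks a mark for initial delivery. This stands as a plausible reading. A reader might infer two rival schedules that cannot both be followed; the documents do not support that, because it requires the columns to run from baseline, which is nowhere stated. The same reading, however, puts the first caregiver measure 4 weeks after delivery, so it does not remove the main consequence.

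Further points, and what remains of each:

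- **Exposure.** A reader might infer that follow-up on intervention is 15% shorter under Table 3. That is only the upper end and needs delivery on the day of baseline. Eligibility assessment, contact, consent, interview, review and case conference all come between, so a smaller gap is likely.
- **AE/SAE interval.** The text's follow-up sentence names no AE/SAE assessment. The 4-week figure combines the text's start with Table 3's safety row. MTM delivery is also not the date of a drug change, since the primary care physician is consulted first. The Human Participants Section cited under Study population is not in the document and may say more.
- **Mixing across sites.** A reader might infer that sites follow different schedules. The document names one institution, so nothing supports this.
- **Typesetting.** The MTM and caregiver rows both lack a baseline mark, and a mark may be misplaced. The MTM row as it stands fits the four columns, so the sponsor should check it.

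**Conclusion.** The inconsistency is real and worth correcting. Table 3, to which the plan refers for timing, shows no initial MTM delivery. The text counts its contacts from such a delivery, and no section fixes the origin.

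Assuming 13 and 26 weeks for 3 and 6 months, first MTM to the 6-month endpoint is 22 to 26 weeks, a gap of 0 to 15% that depends on the undated delivery. The next AE/SAE check is about 9 weeks after a week-4 start, or about 4 weeks after a start near baseline if Table 3's safety row applies.

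The consequence that matters most for analysis is that the caregiver measures may have no pre-intervention value, although the outcome section places them at the start and end of the study.

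It would be tempting to conclude that the primary MAI result or the sample size is compromised. The documents do not support that. The primary endpoint is fixed as baseline to 6 months, its baseline measures come before MTM on any reading, and nothing shows that up to 4 weeks' difference would alter MAI or medication counts.

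**What to change.** 1. State one time zero. Reconcile Table 3 with the AMOR-KY MTM Intervention section and the section Outcome variables (Aims 1 and 2), so that all show the same initial MTM delivery, follow-up contacts and AE/SAE checks. Which clinical schedule applies is for the investigators to decide.
2. Place the first caregiver measure before first MTM delivery, so that its pre-post change is valid. If data collection is complete, report for each caregiver whether the first measure came before or after delivery, and describe the change accordingly.
3. Record the date of first MTM delivery for each participant. Report the intervals from it to the first later AE/SAE check and to the 6-month assessment.

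The cost is a corrected table, one sentence and one date field. The caregiver measure may have to move to an earlier contact; the correction itself need not add a visit and changes neither 34 nor 50.

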Is this the least expensive alternative compared with others of equal utility?	1
Is there unnecessary duplication with other drugs?	1
Is the duration of therapy acceptable?	1

development of our planned larger scale R01 interventional study focused on remote deprescribing interventions in rural and underserved communities throughout distributed US populations.

Expected results & alternative approaches. As this is a single-arm pilot study, we will not be able to distinguish effects of usual care from the additional MTM intervention. However, because usual care in the Cognitive Clinic does not place substantial focus on medications, it is likely that any observed changes will be plausibly attributable to the MTM intervention, and evaluations of feasibility and acceptability will also be distinguishable. Relevant concerns to this study include technology and access issues that may be prohibitive for our rural population. This should be minimized through the availability of telemedicine in their local community health care facilities that afforded the initial telemedicine consultation. Should we discover such barriers to engagement we will leverage internal funding to provide appropriate internet connectivity and or devices as need to ensure the conduct of the trial is not compromised by such concerns or issues. Another possible barrier to the study's conduct and execution of our planned deprescribing intervention includes issues in regard to coordination and acceptability of our proposed medication modifications with the rural primary care providers. This has not been a problem previously but maintaining close communication on our intervention and recommendations is needed to ensure our success. Should this prove an obstacle, further develop initiatives to enhance our integration and cooperativity with the rural primary care physicians that are involved in our participant's care.
